6.2 Randomisation

After completion of the screening phase, the patient will be re-assessed under BTS guidelines and the ASS completed. Blood pressure, respiration rate and oxygen saturations will also be measured. Provided they meet the inclusion criteria, and that written proxy consent has been obtained, the patient will be eligible for randomisation. The time of randomisation will be recorded on the CRF. Patients no longer meeting the criteria are excluded and will continue to be treated as per standard hospital practice. Patients who are randomised will have their contact details (name, address and telephone number) and GP details added to the CRF.

Trial treatment will begin as soon as possible after the initial nebuliser treatment has concluded and assessments have been performed. The clinician should ensure that the duration between obtaining consent, performing assessments and the start of trial treatment does not impact on the well-being of the participant. Treatment kits will be located in a locked cabinet in the department. Provisions should be made to ensure the trial medication is accessible to staff 24 hours a day. Kits will be assigned in sequential order. Details of randomised patients should be entered on the randomisation log kept in the Study Site File and on accountability logs kept with the supply of trial medication.

7 TRIAL TREATMENT/S

7.1 Introduction

This study is designed as a prospective, controlled, double-blind, multicentre, randomised clinical trial comparing the effects of magnesium sulphate versus placebo (isotonic saline) in children with severe acute asthma as defined by BTS guidelines; patients will be randomised to receive nebulised salbutamol 2.5mg (aged 2-5 years) or 5mg (aged 6 years and over) and ipratropium bromide 0.25mg mixed with either 2.5ml of isotonic magnesium sulphate (250mmol/L, tonicity 289 mOsm; 151mg per dose) or 2.5ml of isotonic saline on three occasions at 20 minute intervals.

7.2 Formulation, Packaging, Labelling, Storage and Stability

Supplies will be sourced from St Mary's Pharmaceutical Unit, Cardiff and Vale NHS Trust, who will provide labelled and blinded treatment kits following randomisation lists provided by the MCRN CTU. These will be QP released by from St Mary's Pharmaceutical Unit, Cardiff and Vale NHS Trust. Each will contain three 10ml bottles with 2.5ml magnesium sulphate solution or isotonic saline (placebo) in each bottle. Kits will have an expiry date of two years after manufacture.

Treatment kits will be received by the site pharmacy and dispensed in batches to the participating department where they will be stored in a locked cabinet at $\leq 25^{\circ}$ C. Should there be a temperature excursion above 25°C, the affected kits must then only be stored in the department for a maximum period of three months from the date of the excursion at a temperature not exceeding 30°C. In the event the temperature exceeds 30°C, the affected kits must be withdrawn from use.

The cabinet will contain a calibrated maximum/minimum thermometer to monitor storage conditions. This should be checked daily and the results recorded on the log provided.

The Trial Manager will ensure sites have sufficient supplies based on recruitment projections and should be contacted regarding re-supplies.

7.2.1 Preparation, Dosage and Administration of Study Treatment/s

Patients will receive three consecutive trial treatments of 2.5ml magnesium sulphate solution or placebo at 20-30 minute intervals, interspersed with clinical assessments. Trial treatment will be directly added to a nebuliser containing salbutamol 2.5mg (2-5 years) or 5mg (6 years and over) and ipratropium bromide 0.25mg. No further preparation of the study medication is required. In the event that there is residual volume following 20 minutes of nebulisation, the remainder should be discarded so that assessments can be performed and the next trial treatment delivered as per the schedule outlined in section 8.1.

7.3 Dose Modifications

No dose modification of the study treatment is permitted and dosing will continue in the event of deterioration of the patient's condition unless cessation therapy is deemed necessary by the clinician, or if consent for the trial is withdrawn.

7.4 Accountability Procedures for Study Treatment/s

Site pharmacies will be supplied with sufficient supplies based on initial estimates of recruitment. The Trial Co-ordinator will be responsible for monitoring distribution and facilitate re-supplies where necessary. On receipt of study supplies, the site will fax a confirmation sheet back to the MCRN CTU. This will document that the correct number of treatment kits have been received. If the supplies are retained in the pharmacy, they should be subject to appropriate temperature monitoring as per individual site procedure. The kits will be dispensed to recruiting department and stored in a locked cabinet under the conditions outlined in section 7.2.

At closure of the trial, all used and unused treatment kits will be returned to the pharmacy for destruction.

7.5 Assessment of Compliance with Study Treatment/s

The CRF will record details of the compliance with the dosing schedule. In the event the treatment is not given, the reason will be documented on the CRF.

7.6 Concomitant Medications/Treatments

Additional medications used to treat exacerbation of the patient's condition or used to treat adverse events will be recorded on the concomitant medications page of the CRF. The reason for use, the drug, route of administration, dose and duration of use should be recorded.

7.6.1 Medications Permitted

After entry into the trial no other medications are permitted unless, in the opinion of the clinician, they are required to treat severe deterioration in the patient's condition or to treat adverse events.

7.6.2 Medications Not Permitted/ Precautions Required

No medications are contraindicated for use as a consequence of treatment with the study medication or comparator.

7.6.3 Data on Concomitant Medication

Concomitant medications will be record in the specified section of the CRF. The reason for use, the drug, route of administration, dose and duration of use should be noted.

7.7 Unblinding

7.7.1.1 Procedure

a. The decision to unblind a single case should be made when knowledge of an individual's allocated treatment is essential to enable treatment of serious adverse event/s.

- b. Unblinding envelopes will be provided by the MCRN CTU and will contain details of the treatment allocation. These will be stored securely in an assigned place within the participating A&E department/ paediatric assessment unit.
- c. Where possible, permission to unblind an individual case should be requested via the trial co-ordinator at MCRN CTU. Agreement of the Chief Investigator ([name]), or his agreed delegate, will then be sought.
- d. If unblinding of an individual is deemed necessary, the responsible investigator will select the appropriate envelope to reveal the allocation details of an individual patient only and complete an unblinding CRF which will document:
 - i. Date information needed
 - ii. Detailed reason for unblinding
 - iii. Identity of recipient of the unblinding information

A copy of the unblinding CRF will be forwarded to the MCRN CTU within 24 hours.

- e. The responsible investigator should ensure all necessary CRFs to time of unblinding are completed and submitted to MCRN CTU (if possible, completed *before* unblinding is performed)
- f. All instances of unblinding should be recorded and reported in writing to the MCRN CTU by the local investigator, including the identity of all recipients of the unblinding information.
- g. Allocation should not routinely be revealed to MCRN CTU personnel (not recorded on the unblinding CRF) unless the reason for unblinding meets the criteria as described in section 10.8.1

Accidental Unblinding

All instances of inadvertent unblinding should be recorded and reported in writing to the MCRN CTU by the local investigator. Reports to include:

- 1. Date of unblinding
- 2. Detailed explanation of circumstances
- 3. Recipients of the unblinding information
- 4. Action to prevent further occurrence

Allocation should not be routinely revealed to MCRN CTU personnel

At Trial Closure

The end of the trial will be considered as the date of the final database lock. In the event that the trial is closed prematurely by the trial steering committee, on the recommendation of the independent data and safety monitoring committee, for reasons such as clear differences between safety of trial treatments, the end of the trial will still be considered as the date of the final database lock. Upon trial closure the participating centres will return all unblinding envelopes, without breaking the seals to reveal allocation codes, to the MCRN CTU. MCRN CTU will notify local investigators in writing of unblinding information for patients under their care. A copy of this notification should be placed in the medical records and a copy retained in the site file. The local investigator is responsible for the decision as to whether participants should be informed about the treatment they received.

Individuals that have participated in a trial testing a medicinal product within the three months preceding screening will be ineligible for the MAGNETIC study. To avoid potentially confounding issues, ideally patients should not be recruited into other trials during the one month until final follow up. Where recruitment into another trial is considered to be appropriate and without having any detrimental effect on the MAGNETIC trial this must first be discussed with the coordinating centre (MCRN CTU) who will contact the Chief Investigator ([name]).

8 ASSESSMENTS AND PROCEDURES

8.1 Schedule for Follow-up

Following randomisation, trial participants will be assessed over four hours as is usual clinical practice for this kind of episode. Follow up will continue for those patients who require admission after the initial four hours and will continue until discharge. There will be an additional, post discharge, follow-up at one month via questionnaires sent to the patient's home. Procedures should follow the timelines in table 2 and as listed below. Note that timepoints are for guidance however it is anticipated that timing of dosing and assessments may vary for some patients. The timing of the dose and timing of assessments will be recorded on the CRF.

- 1) Post randomisation (as soon as possible):
 - a. One Vial from the treatment kit will be added to the nebuliser in conjunction with salbutamol 2.5mg or 5mg and ipratropium bromide 0.25mg and nebulised.
- 2) 20mins post randomisation:
 - a. Conclude first nebuliser treatment
 - b. Completion of ASS score (record time of assessment)
 - c. Blood pressure, respiration rate and oxygen saturation
 - d. Review of adverse events and concomitant medications
 - e. Begin second nebuliser treatment (as for first dosing)
- 3) 40mins post randomisation:
 - a. Conclude second nebuliser treatment
 - b. Completion of ASS score (record time of assessment)
 - c. Blood pressure, respiration rate and oxygen saturation
 - d. Review of adverse events and concomitant medications
 - e. Begin third nebuliser treatment (as for first dosing)
- 4) 60mins post randomisation:
 - a. Conclude third nebuliser treatment
 - b. Completion of ASS score (record time of assessment)
 - c. Blood pressure, heart rate, respiration rate and oxygen saturation
 - d. Review of adverse events and concomitant medications
 - e. Treat as per usual practice
- 5) 120mins post randomisation:
 - a. Completion of ASS score (record time of assessment)
 - b. Blood pressure, respiration rate and oxygen saturation
 - c. Review of adverse events and concomitant medications
 - d. Treat as per usual practice
- 6) 180mins post randomisation:
 - a. Completion of ASS score (record time of assessment)
 - b. Blood pressure, respiration rate and oxygen saturation
 - c. Review of adverse events and concomitant medications
 - d. Treat as per usual practice
- 7) 240mins post randomisation:
 - a. Completion of ASS score (record time of assessment)
 - b. Blood pressure, respiration rate and oxygen saturation
 - c. Review of adverse events and concomitant medications
 - d. Treat as per usual practice

- 8) During admission (if applicable)
 - a. Record of asthma medication (further salbutamol treatment/nebulisers/IV)
 - b. Record of procedures/investigations (ventilation/surgery/other tests)
 - c. Review of adverse events and concomitant medication
- 9) Before discharge:
 - a. Review of adverse events and concomitant medications
 - b. Saliva sample for pharmacogenetic substudy (provided written consent is obtained)
 - c. Completion of study outcomes
- 10) 1 month follow up by post:
 - a. Parents receive PedsQL asthma module to complete and return
 - b. Children over 5 receive age-specific PedsQL asthma module to complete and return
 - c. Parents receive the EQ-5D questionnaire to complete (on patient's behalf) and return
 - d. Parents receive a trial specific health care resource utilisation questionnaire to complete and return

Table 2: Schedule of Study Procedures

Procedures		Screening	Randomisation*	20 minutes post Randomisation	40 minutes post Randomisation	60 minutes post Randomisation	120 minutes post Randomisation	180 minutes post Randomisation	240 minutes post Randomisation	During Admission##	Before discharge	1 month follow-up	Premature Discontinuation
Signed Consent F	orm		Х										
Assessment of Eli	gibility Criteria	Х	Х										
Yung's Asthma Se	everity Score	Х	Х	Х	Х	Х	Х	Х	Х				Х
Assignment to stu	dy treatment		Х										
Review of Medical	History	Х	Х										
Review of Concon	nitant Medications	Х	Х	Х	Х	Х	Х	Х	Х	Х	Х		Х
Study Intervention	**		Х	Х	Х								
Blood pressure, Sa	aO ₂ , respiration rate	Х	Х	Х	Х	Х	Х	Х	Х				
Saliva sample for	pharmacogentic substudy#	(X)									(X)		
PedsQL™ Asthma	a Module											Х	
EQ-5D												Х	
Health Economics	Questionnaires											Х	
	Complete	Х											Х
Physical Exam	Symptom-Directed		(X)	(X)	(X)	(X)	(X)	(X)	(X)	(X)	(X)		
Assessment of Ad	verse Events			Х	Х	Х	Х	Х	Х	Х	Х		Х

Patients not randomised to the trial will be asked to consent to the pharmacogenetic sub-study following screening. Randomised patients will be asked to consent to the sub study following scheduled follow up but before they are discharged.

X – Activities required

(X) – As indicated/appropriate.

*At randomisation, all procedures should be done before study intervention.

**Study Intervention – A maximum of 3 doses administered at 20-30 minute intervals. Trial treatment is administered in conjunction with nebulised salbutamol and ipratropium bromide.

^{##} If appropriate

8.2 **Procedures for Assessing Efficacy**

The ASS will be assessed using the most validated score, the Yung $ASS^{2,5,19}$ which comprises three clinical signs; wheezing, accessory muscle use and heart rate (Appendix A). The score has been validated as a measure of asthma severity in children, has been demonstrated to be reproducible and reliable² with good inter-observer agreement and correlates well with oxygen saturations and FEV₁¹⁹. This score is clinically easy to use and involves standard assessments, used routinely by medical and nursing staff while managing acute asthma. The ASS assessment should be carried out by a clinician, or by a nurse who in the opinion of the PI is appropriately trained to make the necessary observations, and who is trained in the use of a stethoscope to detect and assess respiratory wheeze. These individuals will be identified on the delegation of responsibilities log completed at each site. The assessor will also initial the CRF to document who performed the assessment.

8.3 **Procedures for Assessing Safety**

Patient status will be monitored for four hours. Accordingly, oxygen saturation, respiratory rate and blood pressure will be recorded every 20 minutes during the treatment period and details recorded on the CRF. Follow up checks will be performed at 2, 3 and 4 hours following the final study treatment. Other checks may be performed as part of routine medical treatment but will not be recorded on the CRF unless associated with an AE.

8.4 Other Assessments

8.4.1 Quality of Life and Health Economics

Parents will be asked to complete the EuroQol EQ-5D (on their child's behalf) and a questionnaire based around health economic aspects at the one month follow-up (as explained below). Parents and children also will be asked to complete the asthma module of the PedsQLTM Quality of life questionnaire at one month. The PedsQLTM is available in specific age ranges (2-4, 5-7, 8-12 and 13-18 years) and comprises of two reports (parental completion and child completion) for all age ranges apart from 2-4 years. For children aged 2-4 years, only a parental report will be completed. The 1 month follow-up questionnaire distribution will be centrally coordinated by the MCRN CTU and will be designed to maximise response rates. Non-responders will be followed up by sending a reminder letter approximately one week after the initial questionnaires. Should there be no response, they will then contacted by telephone and repeat questionnaires sent if necessary.

A prospective economic evaluation will be conducted alongside the trial with the view to estimating the cost-effectiveness of nebulised magnesium sulphate in the management of severe acute asthma in children. Data will be collected on the health services resources used in the treatment of each child during the time horizon covered by the randomised controlled trial. Data collection forms will record the duration and intensity of care provided to each child, based on standard criteria for level of care, as well as complications experienced. Details of the resources associated with salient clinical events will be recorded. Current UK unit costs will be applied to each resource item to value total resource use in each arm of the trial. A per diem cost for each level of inpatient, outpatient and day care will be calculated by the health economics researcher from detailed questionnaires completed by NHS finance departments, giving cost data and apportioning these to different categories of patient using a 'top-down' methodology. The unit costs of clinical events that are unique to this trial will be derived from the hospital accounts of the trial participating centres, although primary research that uses established accounting methods may also be required. An

incremental cost-effectiveness analysis will be performed and will be expressed as the incremental cost per quality-adjusted life year (QALY) gained. The economic evaluation will be informed, in part, by data collated by economic questionnaires completed by the parents at 4 weeks post-randomisation. These economic questionnaires will detail the use of hospital and community health services by each child following the initial hospital contact, and will provide EuroQol EQ-5D data completed by the parents⁷. Given the methodological limitations surrounding preference-based outcomes measurement in young children¹⁵ it will be necessary to map disease specific outcomes in children aged less than 7 years onto multi-attribute utility measures, such as the EQ-5D⁷.

8.5 Substudies

8.5.1 Pharmacogenetic substudy

Research question

Do β_2 adrenoceptor or muscarinic receptor polymorphisms explain the differences in response to therapy in acute severe asthma in children?

β_2 adrenoceptor gene (ADRB2) and asthma

The β_2 adrenoceptor gene (ADRB2) is located on chromosome 5q31, a region linked to asthma, allergic phenotypes and bronchial hyperresponsiveness. Single nucleotide polymorphisms occur in various positions within the gene, but those that appear to have the greatest effect on receptor function are at amino acid positions 16, 27, 34 and 164 (reviewed 1). Polymorphisms within the 5' leader cistron and the 3' untranslated region are also potential modifiers²⁰. However the majority of studies have concentrated on the most common variations at positions 16 and 27 (Gly16ARArg and Gln27Glu). Although in vitro the Ile164 variant has reduced coupling to adenyl cyclase resulting in shorter duration of receptor activation, its functional effect is limited by its very low frequency in most populations. There is no difference in ligand binding or basal activation of adenyl cylcase between different polymorphisms at codon 16 or 27, but compared to the Arg16 variant, the Gly16 variant shows increased agonist promoted downregulation of receptor expression^{21, 22}.

There appears to be no consistent pattern in β_2 adrenoceptor polymorphisms in the incidence, persistence or severity of asthma. Previous meta-analyses of the association between asthma susceptibility and ADRB2 polymorphisms have given conflicting results, although a recent study combining previous meta-analyses with data from the 1958 British Birth Cohort study reported no association^{23, 24}. Similarly there is conflicting evidence of the effect of ADRB2 polymorphisms on the persistence of symptoms or asthma severity. In a recent cross-sectional survey of 546 Scottish children the risk of an asthma exacerbation was greater in those homozygous for Arg16 compared to those homozygous for Gly16²⁵.

Short acting β_2 agonists (SABAs) are the treatment of choice in acute asthma – often administered at high doses via either a metered dose inhaler and spacer or by nebuliser. In the past SABAs were often administered on a regular basis as maintenance therapy. In contrast long acting β_2 agonists (LABAs) have no role in acute severe asthma, but are increasingly used as maintenance therapy in combination with inhaled steroids.

Retrospective analyses had suggested that individuals homozygous for Arg16 using regular Salbutamol had significantly more exacerbations of asthma, and were significantly more likely to need rescue corticosteroids. In the BARGE (beta adrenergic response by genotype) study patients were recruited on the basis of their ADRB2 genotype, and randomised to receive regular Salbutamol or placebo. During a run in period with minimal Salbutamol use, peak expiratory flow rates (PEFR) were significantly higher in those homozygous for Arg16 compared to those homozygous for Gly16. However when receiving regular four times per day Salbutamol the PEFR of those homozygous for Arg16 decreased significantly, while the peak expiratory flow rate of those homozygous for Gly16 improved significantly. In contrast a number of large

studies (almost all pharmaceutical industry sponsored) report no consistent associations between ADRB2 polymorphisms and asthma outcomes in those receiving regular LABAs.

Muscarinic receptor gene (CHRM1, CHRM2 and CHRM3) and asthma

There are limited data on M2 and M3 polymorphisms in asthma²⁶

Pharmacogenetics of magnesium in asthma

We are unaware of published data on the pharmacogenetics of response to magnesium in asthma. The mode of action of magnesium particularly in severe asthma is unclear, but is possibly due to increased β_2 receptor affinity. In asthmatic patients magnesium infusion resulting in an increase in serum magnesium concentration is associated with a significant leftward shift of the dose-response curve to inhaled salbutamol, but no change in the maximum response²⁷.

Thus there is evidence to suggest that the role of magnesium in severe asthma is via modulation of the β_2 receptor, and it could be hypothesised that this action reverses the recognised down regulation of the receptor by regular β_2 agonists.

The aim of the substudy will be to examine the polymorphisms described above to see if they are associated with:

(i) Whether children respond to the initial nebuliser prior to randomisation and improve sufficiently from the severity of their exacerbation to not fulfil the entry criteria, or whether they remain severe enough to be recruited into the study and receive treatment plus or minus the study treatment.

(ii) The asthma symptom score profile in children who are randomised to nebulised magnesium sulphate as part of the study.

Analysing the clinical details and their clinical response and comparing their polymorphisms may answer the research question: do β_2 adrenoceptor or muscarinic receptor polymorphisms explain the differences in response to therapy in acute severe asthma in children.

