1 PROTOCOL SUMMARY

Title: MAGnesium NEbuliser Trial In Children (MAGNETIC) – A randomised, placebo controlled study of nebulised magnesium in acute severe asthma in children Phase: Ш **Population:** The target population will be children (aged 2-15 years) presenting to hospital emergency departments and acute paediatric inpatient units with severe acute asthma Number of Sites: 30 - 35 sites throughout the United Kingdom **Study Duration:** Total study duration for each child is 240 minutes with a follow-up assessment after one month. Children will be screened at presentation, provided with information about the trial if potentially eligible, and treatment initiated according to BTS guidelines. Twenty minutes after presentation a trial screening assessment will be undertaken

and written informed consent obtained for eligible patients. Trial assessments reflect those routinely performed in this patient population and will be completed at randomisation, prior to administration of randomised therapy, and at 20, 40, 60, 120, 180 and 240 minutes post randomisation. Follow-up questionnaires will be sent to the patient's home one month later.

Description of

Agent/ Intervention: All patients recruited into the study will have standard treatment as per BTS guidelines, plus either nebulised magnesium sulphate or placebo.

Children aged 2-5 years will be randomised to receive nebulised salbutamol 2.5mg and ipratropium bromide 0.25mg mixed with either 2.5ml of isotonic magnesium sulphate (250mmol/L, tonicity 289 mOsm; 151 mg per dose) or 2.5ml of isotonic saline on three occasions at twenty-minute intervals.

Children 6 years and over will receive 5mg of nebulised salbutamol and ipratropium bromide 0.25mg mixed with either 2.5ml of isotonic magnesium sulphate (250mmol/L, tonicity 289 mOsm; 151 mg per dose) or 2.5ml of isotonic saline on three occasions at twenty-minute intervals.

Objectives:

Primary:

Does nebulised magnesium sulphate used as an adjunct to nebulised salbutamol and ipratropium bromide for one hour in children with acute severe asthma result in a clinical improvement in the asthma severity score (ASS) when compared to nebulised salbutamol, ipratropium bromide and placebo?

Secondary:

Does nebulised magnesium sulphate used as an adjunct to nebulised salbutamol and ipratropium bromide for one hour in children with acute severe asthma, when compared to nebulised salbutamol, ipratropium bromide and placebo, have an effect on:

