11.3.1 Informed Consent for Pharmacogenetic Substudy

Informed consent to take a saliva sample for use in the pharmacogenetic substudy will take place at two possible timepoints:

a) At the conclusion of the screening phase, for patients who are not randomised into the main study because:

i. Severity/eligibility criteria were not met before or after the initial nebuliser, or

ii. Consent was not obtained for the main study

b) At conclusion of the follow up (240mins after randomisation), but before the patient is discharged. Parents/legal guardians and patients will be provided with IEC-approved information sheets specifically designed for the sub-study. These will be presented to parents at the earliest opportunity as to provide parents and patients with adequate time to consider the information and ask any questions.

Discussion of objectives and potential inconveniences of participating in the sub-study are to be provided to patients by staff with experience with minors. Parental consent and, if appropriate, patient assent, will be obtained **prior** to collection of the saliva sample. Both the research practitioner taking consent and the parent or legally acceptable representative must personally sign and date the form. If capable, the patient should assent and sign and personally date a separate IEC-approved assent form. The parent or legal representative should also sign and date the assent form. Assent forms do not substitute for the consent form signed by the patient's legally acceptable representative.

The original copy of the signed consent/assent forms will be retained in the Study File and must be made available for inspection. A copy will be returned to the MCRN CTU and one will also be put in the child's notes. A further copy of the signed consent/assent forms will be given to the child's legal representative.

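### Pharmacogenetic aim (ii) is confined to the magnesium arm, so it mixes magnesium, bronchodilator and prognostic gene effects and leaves out placebo children who are sampled anyway

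*Protocol*

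**What the plan says.** Section 8.5.1 asks whether β2-adrenoceptor or muscarinic receptor polymorphisms "explain the differences in response to therapy in acute severe asthma in children". It then sets two aims. Aim (i) concerns response to the initial nebuliser given before randomisation. Aim (ii) concerns "The asthma symptom score profile in children who are randomised to nebulised magnesium sulphate as part of the study". No sentence in the section compares genotype effects between the magnesium and placebo arms.

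Sampling is not limited by arm. The footnote to Table 2 in section 8.1 states: "Randomised patients will be asked to consent to the sub study following scheduled follow up but before they are discharged". Section 11.3.1 places that consent "At conclusion of the follow up (240mins after randomisation), but before the patient is discharged", again without reference to allocation.

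Background treatment is common to both arms. The protocol summary states: "All patients recruited into the study will have standard treatment as per BTS guidelines, plus either nebulised magnesium sulphate or placebo". A second footnote to Table 2 adds: "Trial treatment is administered in conjunction with nebulised salbutamol and ipratropium bromide".

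**The concern.** The genes under study code for the receptors on which salbutamol and ipratropium act. A child's genotype may alter the ASS profile because it changes the response to those drugs, because it marks a different natural course, or because it changes the response to magnesium. All three routes operate in the magnesium arm, and only the last is absent from the placebo arm. The background in section 8.5.1 makes the first two plausible: it reports peak flow differences by ADRB2 genotype with minimal salbutamol use, and changes in opposite directions on regular salbutamol. Neither finding involves magnesium.

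Two things are at stake. If aim (ii) is meant to inform on magnesium, its result cannot be attributed to magnesium. If it is meant to serve the general question about response to therapy, it leaves out about half of the randomised children (allocation is 1:1, section 9.2) for no stated reason.

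**Working it through.** The substudy states no sample size, carrier frequency or effect size, so it has no figure to reproduce. The check has an algebraic part, which needs no assumed values, and an illustration, which does.

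**1. What each contrast estimates.** Let G be genotype (carrier 1, non-carrier 0) and T treatment (magnesium 1, placebo 0):

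ASS = β0 + βT·T + βG·G + βGT·G·T + error

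- Genotype difference in the placebo arm: βG (prognosis plus response to salbutamol and ipratropium).
- Genotype difference in the magnesium arm: βG + βGT.
- Difference between the two: βGT (the magnesium-gene effect).

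The magnesium arm alone gives only the sum βG + βGT.

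**2. The same point by simulation.** 4,000 trials, 250 per arm, SD 1.95 (section 9.4). Assumed: 50% carriers, all children genotyped, two-sided 5% test.

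| True βG | True βGT | Magnesium arm only: estimate, % significant | Two-arm contrast: estimate, % significant |
|---|---|---|---|
| 0.7 | 0 | 0.70, 81% | −0.01, 5% |
| 0 | 0.7 | 0.70, 81% | 0.70, 53% |
| 0.7 | −0.7 | 0.00, 5% | −0.70, 52% |

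The first two rows look identical in the magnesium arm and are told apart only with placebo data. In the third row a real magnesium-gene effect is hidden in the magnesium arm.

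**3. Size when there is no magnesium-gene effect.** Assumed: 20% carriers, equal arms, the same gene effect δ in both arms, SD 1.95. With n children in the magnesium arm:

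SE = 1.95 × √(1/(0.2n) + 1/(0.8n)); rejection = Φ(δ/SE − 1.96) + Φ(−δ/SE − 1.96)

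| Randomised children sampled | n in magnesium arm | SE | δ = 0.3 | δ = 0.5 | δ = 0.8 |
|---|---|---|---|---|---|
| 200 | 100 | 0.488 | 9% | 18% | 38% |
| 300 | 150 | 0.398 | 12% | 24% | 52% |
| 400 | 200 | 0.345 | 14% | 31% | 64% |

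Worked case, 200 sampled and δ = 0.5: SE = 1.95 × √(1/20 + 1/80) = 0.488; 0.5/0.488 = 1.03; rejection ≈ 18%. A simulation for δ = 0.8 with random carrier numbers gives 36%, 51% and 63%, and the interaction test rejects in about 5% throughout.

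**4. Price of the interaction.** Its variance is the sum of two equal within-arm variances, so its SE is √2 times the one-arm SE. With 250 per arm, the effect detectable with 80% power is 2.80 × SE:

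| Carriers (assumed) | One-arm contrast | Interaction |
|---|---|---|
| 50% | 0.69 | 0.98 |
| 30% | 0.75 | 1.07 |
| 15% | 0.97 | 1.37 |

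These are before any loss from non-consent.

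**5. Gain for the general question.** If the gene effect is the same in both arms, pooling them doubles the numbers and divides the SE by √2. With 200 sampled and 20% carriers, the SE falls from 0.488 to 1.95 × √(1/40 + 1/160) = 0.345.

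**The case against.** The strongest reply is that aim (ii) names an association of interest and not a test. It does not exclude placebo data, saliva is sought from both arms, and the model terms could be set in an analysis plan that is not shown. The wording may simply be loose drafting for all randomised children. That is plausible and lowers the weight of the point. It does not remove it: the population of the aim is written into the protocol, and an analysis plan that added placebo children would depart from the aim as stated.

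Second, the research question is general. Under it, a gene effect common to both arms is a true finding, so the rejection rates in step 3 are not false positives for that question. This stands. They are misleading only if read as evidence about magnesium.

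Third, the percentages depend on assumed values. A 0.8-point effect is larger than the 0.5 points that section 9.4 treats as the minimum worthwhile difference, and at 0.3 points the rates are only 9–14%. This also stands, which is why a range is given.

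Two stronger readings are tempting, and the documents support neither:

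- A reader might infer that the protocol commits itself to proving a magnesium-gene interaction. The β2-receptor mechanism is offered only as a possible hypothesis in the background, beside the general research question.
- A reader might infer that aim (i) is contaminated, because section 11.3.1 offers consent to children who were never severe and to those whose families declined the main study. That describes who may be sampled. Aim (i) itself is defined by improving out of the entry criteria after the initial nebuliser, and severity is assessed at presentation (section 6.1) and again after it (section 6.2), so children can be classified correctly.

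**Conclusion.** The point holds as a defect in the wording of aim (ii). The algebra in step 1 needs no assumed values: a genotype association within the magnesium arm cannot separate a magnesium-gene effect from a bronchodilator or prognostic one. The restriction does not serve the general question either.

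The size is illustrative. It rests on assumed 20% carriage, an equal gene effect in both arms, no magnesium-gene effect, and the main trial's SD of 1.95. With 200 to 400 randomised children sampled, the magnesium-only test is significant in roughly 18–31% of substudies at 0.5 points and 36–63% at 0.8 points, against about 5% for the interaction test.

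The consequence is limited. The substudy is optional, separately consented, absent from the endpoint lists in sections 4.2 and 9.3, and in effect exploratory. The trial's primary and secondary analyses are untouched.

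**What to change.** Reword aim (ii) to cover the ASS profile in all randomised children who join the substudy, in both arms, analysed with genotype, treatment and genotype-by-treatment terms. State what each term answers: the interaction addresses magnesium, and the genotype effect estimated from both arms addresses background bronchodilator response or prognosis. If an interaction appears, read the background effect from the placebo arm, because an average over arms would then carry part of the interaction. Label the interaction exploratory.

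The cost is a change of wording and of the substudy analysis, with no new samples, visits or consent steps. The price is precision: the interaction's standard error is about √2 times that of the one-arm contrast, so only large magnesium-gene effects are likely to be detected. Aim (i) needs no change on this account.
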